#### *3.4.1 Best Overall Response (BOR)*

Best Overall Response (BOR) will be determined based on the overall visit responses.

BOR per RECIST v1.1 is defined as the best response in the order of: Complete Response (CR), Partial Response (PR), Stable Disease (SD), Progressive Disease (PD), and Not Evaluable (NE) for patients with measurable disease. The minimum duration of Stable Disease to be considered as the best overall response is 3 weeks from first dose of the study treatment.

iBOR per iRECIST is defined as the best response in the order of: Immune Complete Response (iCR), Immune Partial Response (iPR), Immune Stable Disease (iSD), Immune Confirmed Progression (iCPD), Immune Unconfirmed Progression (iUPD) and NE for patients with measurable disease. The minimum duration of Immune Stable Disease to be considered as the best overall response is 3 weeks from first dose of the study treatment.

#### *3.4.2 Definition of Efficacy Endpoints*

##### *3.4.2.1 Objective Response Rate (ORR)*

Objective Response Rate per RECIST v1.1 (ORR) is defined as the percentage of patients whose BOR is either CR or PR.

iORR per iRECIST is defined as the percentage of patients whose best overall response is either iCR or iPR.

##### *3.4.2.2 Disease Control Rate (DCR)*

Disease control rate (DCR) per RECIST is defined as the proportion of patients whose best overall response is CR, PR, or SD  $\geq$  4 Weeks from first dose.

DCR per iRECIST (iDCR) is defined as the proportion of subjects whose best overall response is an iCR, iPR, or iSD  $\geq$  4 Weeks from first dose.

##### *3.4.2.3 Duration of Response (DOR)*

DOR per RECIST 1.1 will be defined as time from first occurrence of CR or PR to the earliest date of first documented PD or death due to any cause, whichever occurs first. Only patients who achieved either CR or PR will be included in the analysis.

DOR per RECIST v1.1 will be calculated as:

$$\text{DOR (months)} = (\text{Event/censoring date} - \text{first date of CR/PR} + 1) / 30.437$$

The event or censoring date will be determined based on the convention listed in Table 3-1.

Table 3-1: Date of Event or Censoring for DOR per RECIST v1.1

Situation	Date of progression or censoring	Outcome
Death or Disease progression between planned disease assessments	Date of death or first disease assessment showing disease progression, whichever occurs first	Event
Death or disease progression after missing two or more consecutively scheduled disease assessments	Date of last evaluable disease assessment visit without documentation of disease progression before the first missed visit	Censored
Initiation of subsequent treatment before disease progression or death (without disease progression beforehand)	Date of last evaluable disease assessment prior to start of alternate anti-cancer treatment	Censored
Alive and without disease progression	Date of last evaluable disease assessment	Censored

iDOR per iRECIST will be defined as time from first occurrence of iCR or iPR to the earliest date of first documented iCPD per iRECIST, initiation of alternate anti-cancer therapy or death due to any cause, whichever occurs first. If iUPD occurs, but is disregarded because of later iSD, iPR, or iCR, that iUPD date should not be used as the progression event date. In the case of an assessment of iUPD is recorded and no subsequent evaluable iRECIST assessments are recorded, the iUPD event will be treated as confirmed disease progression.

Only patients who achieved either iCR or iPR will be included in the analysis.

iDOR per iRECIST will be calculated as:

$$\text{iDOR (months)} = (\text{Event/censoring date} - \text{first date of iCR/iPR} + 1) / 30.437$$

The event or censoring date will be determined based on the convention listed in Table 3-2.

Table 3-2: Date of Event or Censoring for iDOR per iRECIST

Situation	Date of progression or censoring	Outcome
iUPD provided that iCPD is confirmed at the next assessment on or prior to cutoff date	Date of first disease assessment showing iUPD with iCPD is confirmed at the next assessment	Event
If progression is not confirmed and there is no subsequent iSD, iPR, or iCR due to death or withdrawal	Date of first iUPD with no subsequent iSD, iPR, or iCR due to death or withdrawal	Event
Death reported without iUPD on or prior to cutoff date	Date of death	Event
Death or iUPD after more than one consecutive missed visits	Date of last disease assessment with documented non-iUPD	Censored
No post-baseline disease assessments on or prior to cutoff date	Date of the first dose	Censored

On treatment and without disease progression on or prior to the cutoff date	Date of last evaluable disease assessment with evaluable response	Censored
Initiation of alternate anticancer treatment before disease progression or death (without disease progression beforehand)	Date of last evaluable disease assessment prior to start of alternate anti-cancer treatment	Censored
Alive and withdrew on or prior to cutoff date without disease progression	Date of last evaluable disease assessment with evaluable response	Censored

### 3.4.2.4 Progression Free Survival (PFS)

PFS per RECIST 1.1 will be defined as the time from the first dose date to the earliest date of the first documented PD per RECIST 1.1 assess locally, initiation of alternate anti-cancer therapy, or death due to any cause, whichever occurs first.

PFS per RECIST 1.1 will be calculated as:

$$\text{PFS (months)} = (\text{Event/censoring date} - \text{first dose date of ANV419} + 1) / 30.437$$

For subjects who have not progressed and are still alive at time of data cutoff for study analysis or who are lost to follow-up, PFS will be right censored. The event or censoring date will be determined based on the conventions listed in Table 3-3. .

Table 3-3: Date of Event or Censoring for PFS per RECIST v1.1

Situation	Date of progression or censoring	Outcome
Death or disease progression after one missed tumor assessment	Date of death or first disease assessment showing disease progression	Event
Death or disease progression after missing two or more consecutively scheduled disease assessments	Date of last evaluable disease assessment visit without documentation of disease progression or Date of first dose of study treatment, whichever comes later	Censored
Alive and without disease progression and no initiation of alternate anticancer	Date of last evaluable disease assessment or Date of first dose of study treatment, whichever comes later	Censored
Alive with No (or Non-evaluable) post-baseline disease assessments	Date of the first dose of study treatment	Censored
Initiation of alternate anticancer treatment before disease progression or death (without disease progression beforehand)	Date of last evaluable disease assessment prior to the start of alternate anti-cancer treatment	Censored

iPFS per iRECIST will be defined as the time from the first dose date to the earliest date of the first documented iCPD per iRECIST, initiation of alternate anti-cancer therapy, or death due to any cause, whichever occurs first. If iUPD occurs, but is disregarded because of later iSD, iPR, or iCR, that iUPD date should not be used as the progression event date. In the case of an assessment of iUPD is recorded and no subsequent evaluable iRECIST assessments are recorded, the iUPD event will be treated as confirmed disease progression.

iPFS per iRECIST will be calculated as:

$$iPFS \text{ (months)} = (\text{Event/censoring date} - \text{first dose date of ANV419} + 1) / 30.437$$

For subjects who have not progressed and are still alive at time of data cutoff for study analysis or who are lost to follow-up, iPFS will be right censored. The event or censoring date will be determined based on the conventions listed in Table 3-3.

The PFS and iPFS time will be derived based on the scan/assessment dates and not visit dates to determine progression. Assessments/scans contributing towards a particular visit may be performed on different dates. The following rules will be applied for this calculation:

- Date of radiological progression will be determined based on the earliest assessment/scan dates of the component that triggered the progression.
- When censoring a subject for PFS/iPFS, the subject will be censored at the latest of the Evaluable assessment/scan dates contributing to a particular overall visit assessment.

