4.4 Discontinuation of study treatment

Discontinuation of a patient from study treatment may occur or any of the following reasons:

- The patient or legal representative (such as a parent or legal guardian) withdraws consent;
- Confirmed radiographic disease progression;

Note: A patient may be granted an exception to continue on treatment with confirmed radiographic disease progression if clinically stable or clinically improved. Such cases should be discussed by the Investigator or treating physician with the Sponsor.

Note: In certain circumstances, a patient experiencing disease progression per RECIST without clinical deterioration may be allowed to continue on treatment if the Investigator considers it in the patient's best interest and in agreement between the Investigator and Sponsor. If repeated tumor assessment within 4 to 8 weeks confirms progressive disease, the patient will need to be discontinued permanently from treatment.

- Occurrence of any medical condition or circumstance that exposes the patient to substantial risk and/or does not allow the patient to adhere to the requirements of the Protocol;
- Any SAE, clinically significant AE, DLT, severe laboratory abnormality, intercurrent illness, or other medical condition which indicates to the Investigator that continued participation is not in the best interest of the patient;
- Patients who meet Hy's law will be discontinued from treatment;
- Pregnancy;
- Requirement of prohibited concomitant medication;
- Patient failure to comply with Protocol requirements or study-related procedures;
- The patient is lost to follow-up; or
- Termination of the study by the Sponsor or the regulatory authority.

Patients who discontinue for reasons noted above other than progressive disease will have post-treatment follow-up for disease status until disease progression, initiation of a non-study cancer treatment, withdrawal of consent, or lost to follow-up. In addition, each patient, irrespective of disease progression, will be followed for survival by telephone (or public records when allowed as per local regulation) until death or study termination whichever occurs first. Study staff should make every effort to complete the full panel of assessments scheduled for the End of Study Visit in addition to disease evaluation as noted above (■■■ OR ≤30 days since last

dose of study drug). The reason for patient withdrawal must be documented in the electronic case report form (eCRF).

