8.2.4 Final Analysis of Efficacy

Efficacy analysis will be conducted using the Efficacy Population. The primary outcome (ORR per RECIST) will be presented together with a 95% CI for each treatment arm. Treatment arms with an observed ORR 95% CI with a lower limit above 20% and an upper limit above 40% will be considered for future study. All other outcomes measures will be summarized with the appropriate descriptive statistics.

Additional detail regarding derivation and analysis of efficacy outcomes are provided below:

- ORR per RECIST is defined as the proportion of patients whose best overall response is CR or PR;
- ORR per iRECIST is defined as the proportion of patients whose best overall response is immune CR (iCR) or immune PR (iPR);
- Duration of response (DOR) per RECIST will be calculated for patients with CR or PR as the best overall response. DOR is defined as the number of weeks from the start of the first response (CR or PR) to the first date of progressive disease per RECIST, clinical progression, or death due to any cause. DOR will be summarized descriptively using the Kaplan-Meier method;
- Immune DOR (iDOR) per iRECIST will be calculated for patients with iCR or iPR as the best overall response. iDOR is defined as the number of weeks from the start of the first response (iCR or iPR) to the first date of progressive disease per iRECIST, clinical progression, or death due to any cause. iDOR will be summarized descriptively using the Kaplan-Meier method;
- Disease control rate (DCR) per RECIST is defined as the proportion of patients whose best overall response is CR, PR, or SD; (DCR = CR + PR + SD). DCR will be summarized descriptively;
- Immune DCR (iDCR) per iRECIST defined as the proportion of patients whose best overall response is iCR or iPR or immune SD (iSD) per iRECIST; (iDCR = iCR + iPR + iSD). iDCR will be summarized descriptively;
- PFS is defined as the time from the initiation of study treatment to the first occurrence of disease progression per RECIST or death from any cause, whichever occurs first. PFS will be summarized descriptively using the Kaplan-Meier method;
- Immune PFS (iPFS) is defined as the time from the initiation of study treatment to the first occurrence of disease progression per iRECIST or death from any cause, whichever occurs first. iPFS will be summarized descriptively using the Kaplan-Meier method;

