#### *3.4.4.5 Progression Free Survival*

Unless specified otherwise, the analytical methods described in Section 3.4.4.3 for DOR/iDOR will be used for PFS/iPFS. PFS/iPFS summaries will be presented based on Safety Population.

In addition, the number and percentages of patients experiencing a PFS/iPFS event, types of events, and patients censored will be summarized.

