## 5 CHANGES FROM PROTOCOL-SPECIFIED STATISTICAL ANALYSES

Considering the results of the part 1, with a total of 0 response observed from the 2 monotherapy arms the following analysis will not be performed:

- All analysis related to part 2 (combination dose finding) and part 3 (combination dose expansion) as trial stopped after part 1.
- iRECIST analysis in part 1 (monotherapy dose expansion): due to lack of repeated scans once PD by RECIST is assessed, most of the PDs by iRECIST remained unconfirmed and therefore survival endpoints per RECIST will not be analysed.

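### SAP 3.4.2.4 ends PFS at new anti-cancer therapy while its own Table 3-3 censors it, and Section 5 as worded cancels RECIST PFS

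*SAP*

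**What the plan says.** **PFS definition.** SAP 3.4.2.4 runs PFS from first dose to the earliest of three things: "first documented PD per RECIST 1.1 assess locally, initiation of alternate anti-cancer therapy, or death due to any cause, whichever occurs first".

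**Date rule.** The same section then states: "The event or censoring date will be determined based on the conventions listed in Table 3-3". In Table 3-3, the row for a patient who starts another anti-cancer treatment before progression or death has the outcome Censored, with this date: "Date of last evaluable disease assessment prior to the start of alternate anti-cancer treatment".

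**Protocol.** Section 8.2.4 defines PFS as "time from the initiation of study treatment to the first occurrence of disease progression per RECIST or death from any cause". New therapy is not an event.

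**RECIST duration of response.** SAP 3.4.2.3 measures it "to the earliest date of first documented PD or death due to any cause, whichever occurs first". It has no therapy clause, and its Table 3-1 censors new therapy.

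**Reporting.** SAP 3.4.4.5 plans PFS summaries on the Safety Population, and says that "the number and percentages of patients experiencing a PFS/iPFS event, types of events, and patients censored will be summarized".

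**Section 5.** The second bullet, which is about the iRECIST analysis in Part 1, ends: "most of the PDs by iRECIST remained unconfirmed and therefore survival endpoints per RECIST will not be analysed".

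**The concern.** One section of the SAP gives two answers for the same patient. Followed literally, the definition sentence adds a third, non-protocol event type to the planned table of PFS events. It would also change the event count, and possibly the median, if anyone started new therapy before progression.

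The Section 5 wording raises a different risk: read literally, RECIST PFS is not reported at all. Section 5 records no responses in Part 1, so RECIST duration of response has no patients to analyse. SAP Section 1 says that protocol survival follow-up was stopped. PFS is therefore the main RECIST time-to-event result left in Part 1.

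**Working it through.** The plan states no figure for this point, so there is none to reproduce. The check compares the texts and then illustrates the size.

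**1. Do the two rules differ in substance?** Take a patient with first dose on day 1, last evaluable scan on day 57 without progression, and new therapy on day 85. The SAP formula is (event or censoring date − first dose date + 1) / 30.437.

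- Definition sentence: 85 / 30.437 = 2.79 months, event.
- Table 3-3: 57 / 30.437 = 1.87 months, censored.

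Status and date both differ. The sentence cannot be read as merely saying when observation ends, because the table ends it at an earlier date.

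**2. Which rule do the documents support?**

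| Source | New therapy before progression |
|---|---|
| SAP 3.4.2.4, definition sentence | Endpoint, at therapy start |
| SAP Table 3-3 | Censored, at last prior scan |
| Protocol 8.2.4 | Not an event |
| SAP 3.4.2.3 and Table 3-1 (RECIST DOR) | Not an event; censored |
| SAP Section 5 (declared changes) | No wider PFS definition declared |

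Protocol 4.4 also ends disease follow-up at new therapy ("follow-up for disease status until disease progression, initiation of a non-study cancer treatment"). That fits censoring at the last scan but does not decide the matter. The definition sentence is the outlier.

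**3. Section 5.** The bullet's subject and its reason both concern iRECIST. Protocol Appendix D, Table 23, says that RECIST 1.1 progression needs no confirmation unless equivocal, so unconfirmed iRECIST progression is no reason to drop RECIST PFS. SAP 3.4.4.5 still plans it. The text alone does not prove a slip, but it makes one very probable.

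**4. Event count.** Assume 30 patients (the Part 1 maximum), k of whom start new therapy first, with every other patient progressing or dying. The sentence gives 30 events and the table 30 − k: 27, 24 or 18 for k = 3, 6 or 12.

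**5. Kaplan-Meier PFS at 3 months (illustration).** Assumptions not in the documents: exponential time to progression or death, independent switching, scans every 8 weeks, complete follow-up.

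| Assumed median | Share switching first | Sentence | Table 3-3 |
|---|---|---|---|
| 2.5 months | 10% | 0.55 | 0.59 |
| 2.5 months | 20% | 0.49 | 0.58 |
| 2.5 months | 30% | 0.43 | 0.57 |
| 4 months | 10% | 0.69 | 0.72 |
| 4 months | 20% | 0.64 | 0.72 |
| 4 months | 30% | 0.59 | 0.71 |

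**6. Median PFS (illustration).** Trials of 30 patients were simulated with scans every 1.5 or 2 months and switching either independent of progression or anticipating it. The sentence gave a lower median than the table in every scenario. For nominal switching of 10 / 20 / 40%, the gaps were:

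- True median 2.5 months: 0.25–0.53 / 0.43–0.96 / 0.70–1.97 months.
- True median 4 months, progression dated at scans: 0.62–0.74 / 1.08–1.40 / 2.09–2.93 months.

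The percentages are nominal. In the independent-switching model with scan-dated progression and a 2.5-month median, realised switching was 12–13 / 24–26 / 49–51%, so the largest gaps pool different realised rates.

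**The case against.** The best defence is that 3.4.2.4 largely resolves itself. Just before the reference to Table 3-3, it says that patients alive without progression at cut-off will be right censored. Table 3-3 then has a specific row for new therapy. Only one clause disagrees, and a programmer would probably follow the table. If that clause is a slip, Section 5 had no change to declare. The Section 5 bullet is self-evidently about iRECIST, so the loss of RECIST PFS depends on a reading that few would adopt. PFS is descriptive and secondary in a stopped trial with no hypothesis testing. The size figures rest on an assumed 30 patients, assumed complete follow-up and an assumed switching rate.

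Much of this stands, and it limits the weight of the point. Table 3-3 probably would be applied. The event counts hold only under their stated conditions, because other patients may be censored for missed assessments or the early stop. The median gaps are illustrations.

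It does not remove the contradiction. The right-censoring sentence does not cover a patient who switches and then dies before cut-off, so prose and table do not settle every case together. Both faults sit in operative text that tells the analyst what to count and what to omit, and the correct outcome should not depend on the reader guessing which words to ignore.

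**Conclusion.** The concern holds on both counts.

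- The therapy clause in the PFS definition contradicts Table 3-3 and departs from the protocol without being declared. Censoring is the better-supported rule.
- Section 5 as worded cancels RECIST PFS, very probably by mistake; the documents do not confirm the intent.

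The effect on the event count is k events, where k is the number of patients who started new therapy before progression or death. The documents do not give k, and if it is zero the first fault changes no result. In every scenario examined the definition sentence gave a lower PFS than the table, but the size depends on assumed medians, scan intervals and switching rates.

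Table 3-3 is preferred because it keeps the protocol's two event types, not because censoring is unbiased. With a true median of 2.5 months, progression dated at scans and nominal 40% switching that anticipates progression, the censored median was 4.2–4.4 months, against 3.2–3.5 with no switching.

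This should be fixed, but its reach is limited to a descriptive secondary endpoint.

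**What to change.** - In SAP 3.4.2.4, delete the new-therapy clause from the PFS definition and keep Table 3-3 unchanged.
- In SAP Section 5, change RECIST to iRECIST in the phrase about survival endpoints, and state that RECIST PFS is analysed.
- The same clause appears in the iPFS and iDOR definitions. Removing it there is tidy but changes nothing for Part 1, because Section 5 already drops those analyses.

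The cost is a few words and no new analysis. If the database is already locked, SAP Section 1 gives the route: state in the clinical study report that Table 3-3 was applied and that RECIST PFS was retained.

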#### *3.4.2.5 Overall Survival (OS)*

OS is defined as the time from the date of first dose of ANV419 to date of death for any cause. OS will be calculated as:

$$OS \text{ (months)} = (\text{Death/censor date} - \text{first ANV419 dose date} + 1) / 30.4375$$

Patients who are alive or lost to follow-up as of the data cutoff date will be censored at the date the subject was last known to be alive. The last date known to be alive for each individual subject may be determined using, but not limited to, the following dates recorded on the eCRF:

- AE start and stop dates
- Study treatment start and stop dates
- Laboratory assessment dates
- Dates of vital signs, physical examination, Eastern Cooperative Oncology Group (ECOG) performance status, and electrocardiogram (ECG) assessments
- Disease assessment dates
- Start and stop dates of concomitant medications including procedures and alternative anti-cancer therapy
- Date subject last known to be alive on long-term follow-up

#### *3.4.2.6 Time To Response (TTR)*

TTR per RECIST v1.1 is defined as time from first dose to first response of CR or PR and will be calculated as:

$$TTR \text{ (months)} = (\text{first date of CR/PR} - \text{first treatment date} + 1) / 30.437$$

Analysis of TTR will include only patients who eventually achieve CR or PR. No censoring will be performed.

iTTR per iRECIST is defined as time from first dose to first response of iCR or iPR and will be calculated as:

$$iTTR \text{ (months)} = (\text{first date of iCR/iPR} - \text{first treatment date} + 1) / 30.437$$

Analysis of iTTR will include only patients who eventually achieve iCR or iPR. No censoring will be performed.

